| To evaluate the safety and tolerability of U3-1402 in subjects with advanced or metastatic CRC | 
Title: TEAEs and other safety parameters during the study*
 
Description: Descriptive statistics of safety endpoints
 
Time frame: From the time the subject signs the main study ICF and up to 40 (+ 7) days after the last dose of study drug (ie, 5 half-lives of the ADC/the follow-up period)
 
*Although this is a secondary objective, this is a primary outcome measure.
 | Incidence of TEAEs, SAEs, AESIs (ILD and elevation of aminotransferases and TBL), ECOG PS, vital sign measurements, standard clinical laboratory parameters. AEs will be coded using the most recent version of MedDRA and will be graded using NCI-CTCAE v5.0. | Safety |
| To evaluate HER3 protein expression in tumor tissue and its relationship with efficacy | 
Title: Correlation between HER3 protein expression (as determined by HER3 IHC assay) and efficacy
 
Description: Based on a descriptive summary of the efficacy endpoints and HER3 status, a correlative analysis between HER3 protein expression level (as determined by HER3 IHC assay) and efficacy may be performed.
 
Time frame: Efficacy data are collected at baseline, then from the start of study treatment until disease progression or death, lost to follow-up, or withdrawal of consent by the subject.
 
HER3 data are collected at baseline (archival and pre-treatment tumor biopsy) and at Cycle 2.
 | HER3 protein expression in tumor tissue (as determined by IHC) and correlation with efficacy | Efficacy/ Biomarker |

| Objectives | Outcome Measures | Endpoints | Category |
|---|--|--|---------------------|
| To assess the immunogenicity incidence against U3-1402 | 
Title: Immunogenicity
 
Description: ADA prevalence, incidence, and titer for U3-1402
 
Time frame: Data are collected from the start of study treatment until the end of treatment. Additional timepoints are specified in Table 13.1.
 | 
ADA prevalence: The proportion of all subjects having a confirmed positive ADA sample at any point in time.
 
ADA incidence: The proportion of subjects having treatment-emergent ADA.
 
ADA titer will be determined for confirmed ADA-positive samples.
 
Neutralizing antibodies: When neutralizing assay becomes available confirmed ADA-positive samples may be analyzed for neutralizing activity.
 | Immuno- genicity |

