8.3.3. Biomarker Assessments in Tumor Tissue and Blood Samples

Potential patient selection biomarkers (including HER3 expression using IHC) will be analyzed with the intent of identifying those subjects with advanced or metastatic CRC who will most likely derive clinical benefit from U3-1402, to support future subject selection strategies for advanced or metastatic CRC subjects. These potential biomarkers will be assessed in archival and pre-treatment tumor tissue.

Further exploratory archival, pre-treatment, on-treatment, and end-of-treatment tissue (eg, RNA, DNA, and other immune marker IHC) or blood-based biomarkers (eg, soluble protein markers, circulating free DNA [cfDNA] and circulating free RNA [cfRNA]) will be analyzed based on emerging scientific knowledge to better understand the target disease and also to evaluate the effects of study treatment (pharmacodynamic effect and effects associated with U3-1402 clinical activity). The exploratory biomarker analyses may be performed using methods other than IHC (eg, protein, RNA, or DNA analysis). Blood for biomarkers assessment (eg, soluble protein, markers, cfDNA, cfRNA) should be collected as per the Schedule of Events ([Table 13.1](#)). If consent is obtained to perform the mandatory on-treatment tumor biopsy, a tumor biopsy will be collected on Cycle 2 Day 3. Blood sample for biomarkers will also be collected on Cycle 2 Day 3. If consent is not obtained to perform the mandatory on-treatment tumor biopsy, blood sample for biomarkers will be collected on Cycle 2 Day 1. Moreover, blood samples may be used to measure soluble CRC markers, such as carcinoembryonic antigen, CA 19-9, and C-reactive protein, but not limited to these markers only.

The results from exploratory biomarker research may be pooled with biomarker data from other studies with the investigational product to generate hypotheses to be verified in future studies.

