Distribution of time-to-event endpoints (DoR, PFS, and OS) will be estimated using the Kaplan-Meier method and results will be presented graphically. Median DoR and its 2-sided 95% CIs will be calculated using Brookmeyer and Crowley methods. In addition, the event-free probability at different time points (eg, 3, 6, 9, 12 months) will be estimated with corresponding 2-sided 95% CIs using the Greenwood formula for variance derivation. TTR will be summarized using descriptive statistics. Censoring rules for the time-to-event endpoints (DoR, PFS and OS) will be specified in the SAP.

No formal comparison between the two cohorts is planned.

Descriptive statistics for the best percent change from baseline in the SoD will be provided by cohort, if applicable. A waterfall plot of the best percent change in the SoD and a swimmer's plot for response over time will also be prepared.

The correlation between HER3 protein expression level (as determined by HER3 IHC assay) and efficacy will be assessed.

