11.5.3.3. Biomarker Analyses

HER3 protein expression in tumor tissue (as determined by IHC) may be summarized descriptively, and the correlation with efficacy parameters may be analyzed if data permits.

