11.6. Interim Analyses

For each study cohort, review of the preliminary data from Part 1 will be used to determine whether to open Part 2. The decision to advance from Part 1 to Part 2 will be made separately in Cohort 1 and Cohort 2; the interim futility analysis will be conducted with approximately 24 subjects in Cohort 1 and approximately 12 subjects in Cohort 2 after all subjects have had the opportunity to complete two tumor assessments. The tumor assessment period may be extended if emerging data show responses are occurring later, or if the tumor assessment for the final evaluated subject in each cohort is delayed. At the time of the interim analysis for each cohort, enrollment into the respective cohort will be paused until the determination that criteria for advancement to Part 2 has been achieved. Note it is possible for the futility criterion to be passed before the above specified analysis timing. These analyses will be conducted based on BICR assessment in the FAS.

Cohort 1 Decision Criteria at Interim:

1. If at least 3 responders out of 24 subjects in Cohort 1 are observed, then further enrollment in this cohort may proceed.
2. If 0 or 1 responder out of 24 subjects in Cohort 1 is observed at the interim, then further enrollment in this cohort may stop.
3. If 2 responders out of 24 subjects in Cohort 1 are observed, then a decision will be made, after further review of the data, to either continue or stop further enrollment in this cohort.

Cohort 2 Decision Criteria at Interim:

1. If at least 2 responders out of 12 subjects in Cohort 2 are observed, further enrollment in this cohort may proceed after submission of a protocol amendment which includes the preliminary data from Cohort 2 Part 1.
2. If 0 responder out of 12 subjects in Cohort 2 is observed at the interim, then further enrollment in this cohort may stop.
3. If 1 responder out of 12 subjects in Cohort 2 is observed, then a decision will be made, after further review of the data, to either continue or stop further enrollment in this cohort. Further enrollment will be contingent upon submission of a protocol amendment which includes the preliminary data from Cohort 2 Part 1.

The exact decision rules will depend on the actual number of subjects at the respective interim analysis.

If the criterion to pass futility is met at interim for Cohort 2 but not Cohort 1, all data will be reviewed thoroughly to decide the next step for the study.

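### In Scenario 2 the interim selects the two HER3 groups on the responses that the HER3-efficacy correlation then uses, so a pooled response estimate tends to favour HER3 High even with no HER3 effect

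*Combined protocol and SAP*

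**What the plan says.** Table 2.1 of the protocol lists the relationship between HER3 protein expression and efficacy as a secondary objective, with the wording "a correlative analysis between HER3 protein expression level (as determined by HER3 IHC assay) and efficacy may be performed". Section 11.5.1.2 is firmer: "The correlation between HER3 protein expression level (as determined by HER3 IHC assay) and efficacy will be assessed". Section 11.5.3.3 returns to an optional analysis: HER3 expression "may be summarized descriptively, and the correlation with efficacy parameters may be analyzed if data permits". None of the three gives a method or allows for the interim. Section 11.4 assigns efficacy analyses to the Full Analysis Set, that is, all treated subjects. Section 8.3.3 says that candidate selection biomarkers, HER3 by IHC among them, are analysed "to support future subject selection strategies".

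Section 11.6 sets the interim rules, applied to central-review response in the same analysis set:

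- Cohort 1: "If at least 3 responders out of 24 subjects in Cohort 1 are observed, then further enrollment in this cohort may proceed". At the next lower count, "If 2 responders out of 24 subjects in Cohort 1 are observed, then a decision will be made, after further review of the data".
- Cohort 2: "If 0 responder out of 12 subjects in Cohort 2 is observed at the interim, then further enrollment in this cohort may stop". One step up, "If 1 responder out of 12 subjects in Cohort 2 is observed, then a decision will be made, after further review of the data". At 2 or more, enrolment may proceed after a protocol amendment.

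Table 11.1 gives the Scenario 2 totals: 68 in Cohort 1 and 12 in Cohort 2. Section 11.2 plans no hypothesis test, and Section 11.5.1 plans no formal comparison of the cohorts.

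**The concern.** The variable that decides whether a HER3 group keeps enrolling is the outcome later related to HER3 level. Scenario 2 is reached mainly when Cohort 2 has had few responses and Cohort 1 enough. The Low/Negative group is then left at a low count with no new subjects to move it back toward its true rate, while 44 further unselected subjects pull the HER3 High rate close to its true value. At the interim itself, a go at 3/24 or more (at least 12.5%) together with a stop at 1/12 or fewer (at most 8.3%) forces the ordering.

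Because the analysis is descriptive, the point estimate is the result, and the point estimate is what the selection distorts. Section 8.3.3 intends that result to inform patient selection, so the distortion bears on whether HER3 Low/Negative patients are left out of later studies.

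**Working it through.** **Inputs.** Interim sizes 24 and 12, the count rules, and 44 additional subjects in Part 2 (Sections 11.3 and 11.6). True response rates p of 5% and 20% are the protocol's historical and clinically meaningful values; 10% is an assumed value in between. No HER3 effect means the same p in both cohorts.

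**Reproducing the plan's figures.** Exact binomial tails give P(at least 3 of 24 | 20%) = 88.5%, P(at least 2 of 12 | 20%) = 72.5%, P(0 or 1 of 24 | 5%) = 66.1% and P(0 of 12 | 5%) = 54.0%. All four match Section 11.6.

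**Base case.** Cohort 1 continues at X ≥ 3 of 24, Cohort 2 stops at Y ≤ 1 of 12, and interim counts stand as final for the subjects in Part 1.

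- Expected HER3 High rate = (E[X | X ≥ 3] + 44p) / 68
- Expected HER3 Low/Negative rate = E[Y | Y ≤ 1] / 12, where E[Y | Y ≤ 1] = P(Y=1) / (P(Y=0) + P(Y=1))
- Chance of Scenario 2 = P(X ≥ 3) × P(Y ≤ 1)

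At p = 20%:

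- E[X | X ≥ 3] = (4.8 − 1 × 0.0283 − 2 × 0.0815) / 0.8855 = 5.205, so High = (5.205 + 8.8) / 68 = 20.6%.
- E[Y | Y ≤ 1] = 0.2062 / (0.0687 + 0.2062) = 0.75, so Low/Negative = 0.75 / 12 = 6.25%.
- Gap = 14.4 points (unrounded 20.60 − 6.25 = 14.35). Chance of Scenario 2 = 0.8855 × 0.2749 = 24%.

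The same steps at each rate, with P(High > Low) by enumeration:

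| True rate, both cohorts | High | Low/Neg | False gap (points) | High ahead | High ahead, fixed 68 vs 12, no selection | Chance of Scenario 2 |
|---|---|---|---|---|---|---|
| 5% | 8.1% | 3.2% | +4.9 | 79% | 57% | 10% |
| 10% | 12.0% | 4.8% | +7.3 | 94% | 55% | 29% |
| 20% | 20.6% | 6.3% | +14.4 | 99.9% | 51% | 24% |

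Without selection the expected gap is 0 at every rate.

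**Variants (true rates 5%, 10%, 20%).**

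- Cohort 2 stops only at 0/12: gaps +8.1, +12.0, +20.6 points; High ahead in 100%.
- Cohort 1 also continues at 2/24: gaps +3.6, +6.3, +14.0; High ahead in 72%, 89%, 99.8%.
- Base rule, with 20% of eventual responders appearing after the interim (assumption): gaps +4.5, +6.0, +10.7; High ahead in 77%, 84%, 89%.
- Base rule, linear score over four IHC levels, each cohort split evenly between its two levels (assumption, simulated): association positive in 72%, 78%, 91%.

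**Testing.** Under the base rule, for rates up to 20%, a two-sided 5% test of High versus Low would reject in at most 1.2% (Fisher) or 3.4% (Pearson) of Scenario 2 trials.

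**Within-cohort contrast.** The go/stop rule depends on a cohort's total responders and not on their split between levels. In the same simulation the expected 3+ minus 2+ difference in Cohort 1 is 0.

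**The case against.** The strongest reply has five parts.

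1. A reader might infer that the stopping rule fixes the sign, so that Scenario 2 must show a HER3 effect. The documents do not support that. The Section 11.6 rules say may, the exact rule depends on the actual numbers, and PK or subject and disease characteristics may also weigh. Cohort 2 could stay closed with 2 or more responders. At a true rate of 5%, HER3 High leads in 72% to 79% of trials when 1/12 also stops, against 57% with no selection at all. This stands, and the point is worded accordingly.
2. Interim counts are not final. The interim needs only the opportunity for two assessments (about 12 weeks), responses need confirmation at least 4 weeks later, and the primary cut-off requires at least 9 months of follow-up or earlier discontinuation from the study. Later responses narrow the gap, as the variant shows, but do not remove it.
3. The analysis is descriptive and imprecise: the exact 95% intervals are 0 to 26.5% for 0/12 and 0.2% to 38.5% for 1/12, and both contain 20%. This limits overinterpretation but does not remove bias from the estimate.
4. No section prescribes a pooled, unstratified correlation, and methods are left to an SAP due before database lock. That is correct. It makes this a gap to fill before that SAP is final, and not an error already committed.
5. A reader might infer that the between-cohort difference carries no information. It does: 0/12 has probability 54% at a true rate of 5% and 6.9% at 20%. It should be reported, with its bias stated.

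**Conclusion.** The point holds as a conditional bias in one analysis. In Scenario 2 a pooled response-by-HER3 estimate tends to favour HER3 High with no HER3 effect present, by an expected 4.9 to 14.4 points over true rates of 5% to 20%. The direction is certain only if Cohort 2 ends at 0/12. The figures assume equal true rates, the stated count rules applied without other considerations, and no responses after the interim. They cover response rate only: no bias has been shown for DoR, DCR, PFS or OS. The primary analysis, reported by cohort with exact intervals, is not the subject of this point. It is a cheap improvement to an analysis meant to inform patient selection.

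**What to change.** - In Section 11.5.1.2 and the SAP, add a HER3-response analysis stratified by cohort, using the recorded IHC levels. In Scenario 2 this rests essentially on 3+ versus 2+ in Cohort 1, because the 1+ versus 0 stratum will have almost no responders.
- In Scenario 1, also analyse all four levels in Part 2 subjects alone, whose responses played no part in the interim decision. In Scenario 2, restricting to Part 1 does not help, since the selection is strongest there.
- In Scenario 2, report the High-versus-Low difference with the exact intervals for each group and a statement that it is conditional on the interim decision and biased toward HER3 High, giving the size of that bias. Do not present the pooled correlation alone as support for HER3 selection.
- Reconcile the optional and firm wordings in Table 2.1, Section 11.5.1.2 and Section 11.5.3.3.

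The cost is SAP wording and one stratified analysis of data already collected. The downside is that the within-cohort contrast is less precise and covers fewer IHC levels than the pooled one.

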3. STUDY DESIGN

3.1. Overall Design

This is a Phase 2, multicenter, open-label, 2-cohort study of U3-1402 single agent therapy in subjects with advanced or metastatic CRC who are resistant, refractory, or intolerant to at least 2 prior lines of systemic therapy that must include all of the following agents: fluoropyrimidine, irinotecan, platinum agent, an anti-EGFR agent (if clinically indicated), an anti-VEGF agent (if clinically indicated), an immune checkpoint inhibitor (if clinically indicated), and a BRAF inhibitor (if clinically indicated). [Figure 3.1](#) shows the study design.

This study will be conducted at approximately 40 sites in the United States, Europe, and Asia (including Japan). Additional sites may be added as needed.

Figure 3.1: Study Design Schema

- a. Treatment with U3-1402 in all cohorts will continue until the time of progressive disease (PD), unacceptable toxicity, withdrawal of consent, death, termination of the study by Sponsor, or the occurrence of any of the other events specified in Section 5.7.
- b. An interim futility analysis will be conducted after approximately 24 subjects in Cohort 1 have had the opportunity to complete two tumor assessments. Separately in Cohort 2, an interim futility analysis is planned with approximately 12 subjects. For further details, see Section 11.6.
- c. A total of 44 subjects will be enrolled in Part 2. For details regarding sample size in Part 2, see Section 11.3.

BICR = blinded independent central review; CRC = colorectal cancer; DCR = disease control rate; DoR = duration of response; EGFR = epidermal growth factor receptor; HER3 = human epidermal growth factor receptor 3; IHC = immunohistochemistry; IV = intravenous; ORR = objective response rate; OS = overall survival; PD = progressive disease; PFS = progression-free survival; Q3W = every 3 weeks; RECIST = Response Evaluation Criteria in Solid Tumors; TTR = time to tumor response; VEGF = vascular endothelial growth factor.

Part 1

Archival tumor biopsy and pre-treatment tumor biopsy will be collected from all subjects at screening and HER3 protein expression will be measured by an investigational device (HER3 IHC assay).

Subjects may be exempted from the requirement to provide a pre-treatment tumor biopsy if the archival tumor tissue:

- Was collected within 3 months of screening during or after treatment with the last prior cancer treatment and
- Is of sufficient quantity, defined as 2 cores or 20 slides with adequate tumor tissue content.

Results of the prospective HER3 IHC assay from the pre-treatment tumor biopsy will be used to assign subjects into 1 of 2 cohorts:

- Cohort 1: HER3 High (IHC 3+, 2+) (approximately 24 treated subjects), **or**
- Cohort 2: HER3 Low/Negative (IHC 1+, 0) (approximately 12 treated subjects).

See Section 8.3.1 for additional details regarding the HER3 IHC assay.

Subjects will be treated on Day 1 of each 21-day cycle with U3-1402 5.6 mg/kg IV.

For each study cohort, review of the preliminary data from Part 1 will be used to determine whether to open Part 2. The decision to advance from Part 1 to Part 2 will be made separately in Cohort 1 and Cohort 2; the interim futility analysis will be conducted with approximately 24 subjects in Cohort 1 and approximately 12 subjects in Cohort 2 after all subjects have had the opportunity to complete two tumor assessments. The tumor assessment period may be extended if emerging data show responses are occurring later, or if the tumor assessment for the final evaluated subject in each cohort is delayed. At the time of the interim analysis for each cohort, enrollment into the respective cohort will be paused until the determination that criteria for advancement to Part 2 have been achieved. Note it is possible for the futility criterion to be passed before the above specified analysis timing. These analyses will be conducted based on BICR assessment in the Full Analysis Set (FAS).

After review of the data from Part 1 based on criteria outlined in Section 11.6, if the Sponsor decides to enroll subjects irrespective of HER3 expression status in Part 2 (ie, Scenario 1 below, continuing enrollment of Cohort 2 into Part 2), the decision and preliminary data from Cohort 2 Part 1 will be provided as part of a protocol amendment.

Part 2

- Dose: U3-1402 5.6 mg/kg IV Q3W
 - **Scenario 1:** Enrollment continues in Cohort 1 and Cohort 2: approximately 44 subjects will be enrolled, regardless of HER3 IHC status, and receive treatment with U3-1402.

Total sample size at end of study: approximately 80 = Part 1 (Cohort 1 [approximately 24 subjects] + Cohort 2 [approximately 12 subjects]) + Part 2 (Cohorts 1 and 2 [approximately 44 subjects])
 - **Scenario 2:** Enrollment continues in Cohort 1 only: approximately 44 subjects with HER3 High (IHC 3+, 2+) status will be enrolled and receive treatment with U3-1402.

Total sample size at end of study: approximately 80 = Part 1 (Cohort 1 [approximately 24 subjects] + Cohort 2 [approximately 12 subjects]) + Part 2 (Cohort 1 [approximately 44 subjects])

Treatment with U3-1402 in all cohorts will continue until the time of PD (confirmed by BICR) per RECIST v1.1, unacceptable toxicity, withdrawal of consent, death, termination of the study by Sponsor, or the occurrence of any of the other events specified in Section 5.7. If progressive disease is suspected by Investigator tumor assessment, imaging must be submitted to BICR for expedited confirmation of disease progression. The decision to discontinue U3-1402 is according to Investigator judgment and should consider BICR assessment.

3.1.1. Duration of the Study

The study start date is the date when the first subject has signed an informed consent form (ICF).

The enrollment period is approximately 15 months. It will occur in 2 parts separated by an interim futility analysis for each cohort. The estimated treatment period is approximately 8 months, and the follow-up period is approximately 4 months.

The total estimated duration of the study is approximately 27 months. The primary analysis data cut-off will occur when all subjects have had either a minimum of 9 months of follow-up or have discontinued from the study earlier. The DCO may be shifted if emerging data indicate responses are occurring at a different time. The final analysis will be performed after all subjects have discontinued from the study for any reason. In addition, the Sponsor may terminate the study at any time and study termination may also be requested by a competent authority; in such an instance the data cut-off date will be the date of study termination.

3.1.2. Duration of Subject Participation

The screening period is up to 35 days. Each cycle of treatment will be 21 days. The number of treatment cycles with U3-1402 is not limited. Subjects may continue study treatment until the time of progressive disease per RECIST v1.1, unacceptable toxicity, withdrawal of consent, death, termination of the study by Sponsor or the occurrence of any of the other events specified in Section 5.7. If PD is suspected by Investigator tumor assessment, imaging must be submitted to BICR for expedited confirmation of disease progression. The decision to discontinue U3-1402 is according to Investigator judgment and should consider BICR assessment.

Tumor assessments will be performed every 6 weeks (\pm 7 days) from Cycle 1 Day 1 for the first 24 weeks then every 12 weeks (\pm 7 days) thereafter, independent of treatment cycle, until documented disease progression by BICR per RECIST Version (v) 1.1 , death, lost to follow-up, or withdrawal of consent.

There is an End-of-Treatment (EOT) Visit that takes place within 7 days after the final dose of U3-1402 or before the start of new anticancer treatment, whichever comes first. Subjects will be asked to attend a 40-Day Follow-up (F/U) Visit (+7 days) 40 days after the last U3-1402 administration. If the subject begins another anticancer therapy before the end of the 40 days (+7 days), every effort will be made to complete all of the F/U assessments prior to starting the new therapy. For further details concerning assessments performed at the EOT and F/U Visits refer to the Schedule of Events ([Table 13.1](#)).

After discontinuation from study treatment, follow-up information for determining anti-drug antibodies (ADAs) as well as survival information and subsequent anticancer therapy, if available, should be collected every 3 months (\pm 14 days). Survival F/U contact can occur via telephone contact or unscheduled visit and will continue until death, withdrawal of consent, lost

to follow-up, or study closure, whichever occurs first. Refer to [Table 13.1](#) for details. Subjects who discontinue study treatment for any reason other than documented disease progression by BICR, death, lost to follow-up, or withdrawal of consent by the subject will continue to undergo tumor assessments at the same frequency of every 6 weeks (± 7 days) from Cycle 1 Day 1 for the first 24 weeks then every 12 weeks (± 7 days) during the follow-up period.

